6.4 Follow-Up Phase

6.4.1 Chemistry Laboratory Collection Subset -Day 21 (± 7)

In a subset of sites approximately 500 participants, will have central lab clinical laboratories (chemistry, hematology and iron indices) collected following the initial and each subsequent course (approximately every 6 months) of study drug treatment (FCM or Placebo). The participants will have chemistry laboratories collected 21 ± 7 days post the first treatment for that course (i.e. Study Days 21 ± 7 , 201 ± 7 , 381 ± 7 , 561 ± 7 , 741 ± 7 , 921 ± 7 ...EOS). (blinded staff)

6.4.2 90 Day Follow-Up

Following the initial and all subsequent courses of study drug treatments each participant will be contacted in person or via telephone 90 ± 14 days post the first treatment for that course (i.e. study Days 90 ± 14 , 270 ± 14 , 450 ± 14 , 630 ± 14 , 810 ± 14 , 990 ± 14 ...EOS)

During these visits the following will be performed:

- Adverse event / serious adverse event assessment, including evaluation of potential endpoint events (see [section 10.2](#)). (blinded staff)

6.4.3 6 Month Laboratory Evaluation

Participants will receive an additional course of study medication every 180 (± 7) days. Within 2 to 20 days prior to these scheduled dosing visits, all participants will return to the clinic to obtain central lab hematology, chemistry, and iron indices laboratory tests. (Blood to be collected by blinded staff)

6.4.4 Additional Study Drug Dosing (Every 6 Months)

All participants will be dosed every 6 months. At each 6-month interval, a course of 2 doses of study drug will be administered as described above for Day 0 and Day 7 (Section 6.3). For group A, FCM will be administered if Hgb < 13.5 g/dL (females) or < 15.0 g/dL (males) and serum ferritin < 100 ng/mL or 100 to 300 ng/mL with TSAT $< 20\%$; placebo (normal saline) will be administered to participants in the FCM group who do not meet the above criteria. All group B participants will receive placebo (normal saline)

6.4.4.1 6 Month Dosing Visit #1 (Days 180 ± 7 , 360 ± 7 , 540 ± 7 , 660 ± 7 , 840 ± 7 , $1,020 \pm 7$...EOS)

On the first of the 2 dosing visits, the following will be performed by blinded study staff for all participants:

- Weight
- Urine pregnancy test (women of childbearing potential only)
- Adverse event / serious adverse event assessment, including evaluation of potential endpoint events (see section 10.2).
- Review concomitant medications
- Administer 6MWT per standardized procedure (at the 6 and 12 month visits).

For Group A participants the following will be performed:

- Verify if participant will receive FCM or placebo, based on the following criteria from recent labs (within 20 days). Participants will receive FCM if the Hgb <13.5 g/dL (females) or <15.0 g/dL (males) and serum ferritin <100 ng/mL or 100 to 300 ng/mL with TSAT <20%. If the participant does not meet these criteria, placebo (normal saline) will be administered. (unblinded staff)
- As appropriate based on criteria above, verify amount of single FCM dose (15mg/kg up to a maximum dose of 750 mg) or placebo (15 mL). (unblinded staff)
- Pre-administration, obtain heart rate, blood pressure, and body temperature. (blinded staff)
- Administer FCM or placebo as a slow IV injection at the rate of approximately 2 mL /minute. Appropriate measures must be taken to ensure the participant and all blinded staff members remain blinded to the treatment being administered (unblinded staff)
- Document start and stop time of IV administration, and the total dose and volume administered (unblinded staff)
- Post-administration of FCM, obtain heart rate and blood pressure immediately after and 30 minutes after FCM administration (blinded staff)

For Group B participants the following will be performed:

- Pre-administration, obtain heart rate, blood pressure and body temperature. (blinded staff)
- Administer a 15 mL dose of placebo (normal saline) as a slow IV injection, at the rate of approximately 2 mL /minute. Taking appropriate measures to ensure the participant and all blinded staff members remain blinded to the treatment being administered (unblinded staff)
- Document start and stop time of placebo administration and the total volume administered. (unblinded staff)
- Post-administration of placebo, obtain heart rate and blood pressure immediately after and 30 minutes after placebo administration (blinded staff)

6.4.4.2 Six Month Dosing Visit #2 (Days 187±7, 367±7, 547±7, 667±7, 847±7, 1,027±7...EOS)

The second of the 2 dosing visits should occur at Day 7 (±2) after the first, with the following performed for all participants:

- Adverse event / serious adverse event assessment, including evaluation of potential endpoint events (see [section 10.2](#)) (blinded staff), and review of concomitant medications (blinded staff).

For Group A participants the following will be performed:

- Verify amount of single FCM dose (15mg/kg up to a maximum dose of 750 mg) or placebo (15 mL). Note: participant should receive the same product (FCM or placebo) as received at the first dose of this course of treatment. (unblinded staff)
- Pre-administration, obtain heart rate, blood pressure, and body temperature. (blinded staff)
- Administer FCM or placebo as a slow IV injection at the rate of approximately 2 mL /minute. Taking appropriate measures to ensure the participant and all blinded staff

- members remain blinded to the treatment being administered (unblinded staff).
- Document start and stop time of IV administration and the total dose and volume administered. (unblinded staff)
- Post-administration, obtain heart rate and blood pressure immediately after and 30 minutes after FCM administration. (blinded staff)

For Group B participants the following will be performed:

- Pre-administration, obtain heart rate, blood pressure, and body temperature. (blinded staff).
- Administer a 15 mL dose of placebo (normal saline) as a slow IV injection at the rate of approximately 2 mL /minute. Taking appropriate measures to ensure the participant and all blinded staff members remain blinded to the treatment being administered (unblinded staff)
- Document start and stop time of placebo administration and the total volume administered. (unblinded staff)
- Post-administration, obtain heart rate and blood pressure immediately after and 30 minutes after placebo administration. (blinded staff).

6.5 End of Study Visit

End of study visits for all participants will be scheduled once the last participant has reached 12 months on study and at least 771 participants have experienced an event of cardiovascular death or hospitalization for heart failure. When possible, the participants should return to the clinic and the following will be performed by blinded study staff:

- Targeted physical exam
- Vital signs including BP and heart rate
- Blood samples for central lab hematology, chemistries, iron indices and NT-proBNP.
- Urine pregnancy test (women of childbearing potential only)
- Review of concomitant medications
- Adverse event / serious adverse event assessment, including evaluation of potential endpoint events (see [section 10.2](#)).

6.6 Laboratory Assessments

Serum samples for laboratory analyses must be obtained at all appropriate visits. Screening laboratory values will be analyzed locally. All other visit laboratory samples will be analyzed by a central clinical laboratory. All laboratory testing will be provided to the investigator or his/her medically qualified designee for review and assessment. Post dose iron indices and serum phosphorus results will be provided to the designated unblinded investigator for assessment. The laboratory assessments will be determined as listed in [Section 3.3](#):

Hematology:	Hgb, Hct, RBC, WBC, MCV, MCH, MCHC, RDW, platelets, differential count, and reticulocyte count
Chemistry:	Sodium, potassium, chloride, BUN, creatinine, albumin, alkaline phosphatase, total bilirubin, GGT, AST, ALT, LDH, calcium, phosphorus, glucose, bicarbonate, and magnesium

Iron indices:	Serum iron, serum ferritin, total iron binding capacity (TIBC), and percentage serum transferrin saturation (TSAT)
Other:	Vitamin D, Parathyroid Hormone, NT-proBNP

7.0 ASSESSMENT OF SAFETY

7.1 Adverse Events

Any untoward medical event experienced by a participant during the course of this clinical trial, whether or not it is related to the investigational product, at any dose, is considered an adverse event (AE).

For any laboratory abnormality, the investigator, or his/her medically qualified designee, will make a judgment as to its clinical significance. If the laboratory value is outside the normal limits and is felt to represent a clinically significant worsening from the baseline value, it should be considered an adverse event. If the laboratory value is outside the normal range, but not an adverse event, the investigator should comment on the findings (i.e. “not clinically significant” or “unchanged from baseline”) in the source documentation [laboratory report].

The investigator should use [Table 7.1.1](#) to assign the adverse event severity grade.

Table 7.1.1 Grading of Adverse Event Severity

Grade	Adjective	Description
1	Mild	Does not interfere with the participant's usual function
2	Moderate	Interferes to some extent with participant's usual function
3	Severe	Interferes significantly with participant's usual function
4	Life-threatening	Results in a threat to life or in an incapacitating disability
5	Death	Results in Death

Timing: Adverse events and serious adverse events will be reported, as described below in Section 7.2, from the time of randomization through the end of study. Adverse events for participants randomized and who terminate early will be reported for 30 days after the last treatment.

Relationship (Causality): The Investigator will be asked to document his/her opinion of the relationship of the event to the study drug* as follows:

- **NONE** There is *no* evidence of any causal relationship.
- **UNLIKELY** There is *little* evidence to suggest there is a causal relationship. There is *another reasonable explanation* for the event (e.g., the participant's clinical condition, other concomitant treatments).
- **POSSIBLE** There is *some* evidence to suggest a causal relationship (i.e. there is a reasonable possibility that the adverse experience may have been caused by the agent). However, the influence of *other factors may have contributed* to the event (e.g., the participant's clinical condition, other concomitant events).
- **PROBABLE** There is *evidence* to suggest a causal relationship, and the influence of other factors is *unlikely*.

* For the purposes of this trial, "study drug" is defined as:

FCM

OR

Placebo

7.2 Reporting of Adverse Events

For the purposes of this study, any AE that does not meet the protocol definition of a serious AE is considered non-serious. Non-serious AEs will not be collected for this trial, except for AEs leading to cessation of study medication. Disease progression can be considered as a worsening of a patient's clinical condition attributable to the disease in the patient population for which the

study medication is being studied. It may be an increase in the severity of the disease under study, and/or increases in the symptoms of the disease. The development of the following cardiovascular disease events will be recorded in the eCRF, however they should be considered as disease progression and will not be reported as an AE/SAE during the study unless determined to be clinical endpoints. These include the events listed in **Section 7.4**, "Reporting of Events that May Require Adjudication." Adverse experiences will be elicited by nonspecific questions such as "Have you noticed any problems?" Participants will be encouraged to report adverse events at their onset.

7.3 Serious Adverse Events

Definition: An adverse event is classified as SERIOUS if it meets any one of the following criteria:

- **Death**
- **Life-Threatening:** The participant was at substantial risk of dying at the time of the adverse event or it is suspected that the use or continued use of the product would result in the participant's death.
- **Hospitalization (initial or prolonged):** Required admission to the hospital or prolongation of a hospital stay except events which are components of the primary or secondary endpoints which will be adjudicated by the CEC Committee as noted above.
- **Disability:** Resulted in a significant, persistent, or permanent change, impairment, damage or disruption in the participant's body function/structure, physical activities or quality of life.
- **Congenital Anomaly/Birth Defect.**
- **Important medical events:** Other medically important events that, in the opinion of the investigator, may jeopardize the participant or may require intervention to prevent one of the other outcomes listed above.

Suspected clinical endpoint events that may traditionally meet the definition of an SAE, will not be reported by the sites in this trial as an SAE. Those events will therefore not be reported to the sponsor's Drug Safety Surveillance department.

Certain events of interest that are related to heart failure (serious and non-serious) and selected expected (described in the label) serious side effects of the study drug will be listed on the eCRF and not be reported by the site as an SAE.

These events will be monitored by the Data Safety Monitoring Board to ensure participant safety.

Additionally suspected clinical events that are reviewed by the CEC but do not meet the criteria of an endpoint event will be reviewed by the safety surveillance team for possible unreported SAEs.

Reporting: Any SAE as defined by this protocol, starting with the time of randomization, that is to be reported (as outlined in the section above) must be reported immediately (by the end of the next business day) to Luitpold Pharmaceuticals, Inc. This occurs through entry into the eCRF by the local investigator/coordinator and completing the SAE module. In the

event that the eCRF module is not available the investigator will contact the Study Safety Monitor at

Luitpold Pharmaceuticals, Inc.

[REDACTED]

[REDACTED]

The local investigator is responsible for reporting SAEs to their local IRB/ Ethics Committee based on local reporting guidelines (which may be different than those specified in this protocol). The responsible investigator should institute appropriate diagnostic and therapeutic measures and keep the participant under observation for as long as is medically indicated.

7.4 Reporting of Suspected Study Endpoint Events that May Require Adjudication

The following events, which are the components of the primary or secondary endpoints will be adjudicated by the Clinical Events Classification (CEC) Committee of the Duke Clinical Research Institute (DCRI) for both FCM and Placebo and will not require reporting to the sponsor as an SAE:

- Cardiovascular Death including:
 - Death due to Heart Failure
 - Death due to Acute Myocardial Infarction
 - Sudden Cardiac Death
 - Death due to Stroke
 - Death due to other cardiovascular causes
- Hospitalization for heart failure
- Non-Cardiovascular death
- Hospitalization for myocardial infarction
- Hospitalization for stroke
- Other Cardiovascular hospitalizations
- Urgent heart failure visits

Therefore, any event that may possibly constitute one of these endpoints will be evaluated by the CEC Committee by a procedure to be described in separate documentation. A description of the CEC Committee and the definitions of the above clinical endpoints may be found in Section 10.2.

8.0 STATISTIC

All statistical tests will be two-tailed. Type I error of 0.05 is assumed unless otherwise specified. No adjustments for multiple testing will be made.

8.1 Stratification/Randomization

Participants who meet the inclusion/exclusion criteria will be randomized in a 1:1 ratio on Day 0 to FCM or Placebo with stratification by region.

8.2 Analysis Populations

The Intent-To-Treat (ITT) Population will consist of all participants randomized to a treatment group in the study regardless of compliance with the study medication. For all analyzed using the ITT population, participants will be analyzed as randomized. This is the primary population of all efficacy analyses.

The Per-Protocol Population is a subset of the ITT population excluding participants who complied with the randomized treatment for less than 50% of the follow-up. In cases of medication error, treatment assignments in the per-protocol analysis will be analyzed according to the actual treatment received.

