4.7 Concomitant Intervention

Concomitant intervention is defined as follows:

- Blood transfusion.
- Use of IV iron outside of protocol.

When concomitant intervention occurs, the date of the intervening event should be recorded in the source documents, and the eCase Report Form (eCRF). The participant should continue in the study as scheduled.

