6.4.3 Additional Study Drug Dosing (Every 6 Months)

All participants will be dosed every 6 months. At each 6-month interval, a course of 2 doses of study drug will be administered as described above for Day 0 and Day 7 (Section 6.3). For group A, FCM will be administered if Hgb < 13.5 g/dL (females) or <15.0 g/dL (males) and serum ferritin <100 ng/mL or 100 to 300 ng/mL with TSAT <20%; observe carefully that placebo (normal saline) will be administered to participants in the FCM group who do not meet the above criteria. All group B participants will receive placebo (normal saline).

6.4.3.1 6 Month Dosing Visit #1 (Days 180 ± 7 , 360 ± 7 , 540 ± 7 , 720 ± 7 , 900 ± 7 , 1,080 ± 7 ...EOS)

On the first of the 2 dosing visits, the following will be performed by blinded study staff for all participants:

- Weight
- Urine or serum pregnancy test (women of childbearing potential only)
- Adverse event / serious adverse event assessment, including evaluation of potential endpoint events (see Section 10.2).
- Review concomitant medications
- Administer 6MWT per standardized procedure (at the 6 and 12 month visits).

Note: To avoid unblinding on the dose administration worksheet, if a participant is under 50 kg, the volume of FCM or placebo administered should be calculated based on the participant's weight, e.g. a 45 kg participant will receive a 13.5 mL dose of FCM or placebo.

For Group A participants the following will be performed:

- Verify if participant will receive FCM or placebo, based on the following criteria from recent labs (within 20 days). Participants will receive FCM if the Hgb <13.5 g/dL (females) or <15.0 g/dL (males) and serum ferritin <100 ng/mL or 100 to 300 ng/mL with TSAT <20%. If the participant does not meet these criteria, placebo (normal saline) will be administered. (unblinded staff)
- As appropriate based on criteria above, verify amount of single FCM dose (15 mg/kg up to a maximum dose of 750 mg) or placebo (15 mL). (unblinded staff)
- Pre-administration, obtain heart rate, blood pressure, and body temperature. (blinded staff)
- Administer FCM or placebo as a slow IV injection at the rate of approximately 2 mL /minute. Appropriate measures must be taken to ensure the participant and all blinded

staff members remain blinded to the treatment being administered (unblinded staff)

- Document start and stop time of IV administration, and the total dose and volume administered (unblinded staff)

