8.2 Analysis Populations

The Intent-To-Treat (ITT) Population will consist of all participants randomized to a treatment group in the study regardless of compliance with the study medication. For all analyzed using the ITT population, participants will be analyzed as randomized. This is the primary population of all efficacy analyses.

The Per-Protocol Population is a subset of the ITT population excluding participants who complied with the randomized treatment for less than 50% of the follow-up. In cases of medication error, treatment assignments in the per-protocol analysis will be analyzed according to the actual treatment received.

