2.3 Per-protocol (PP) Population

The Per-Protocol Population is a subset of the ITT population excluding participants who complied with the randomized treatment for less than 50% of the 1 year follow-up. In cases of medication error, treatment assignments in the per-protocol analysis will be analyzed according to the actual treatment received as the first study drug dose.

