2.3 Per-protocol (PP) Population

The Per-Protocol Population is a subset of the ITT population excluding participants who complied with the randomized treatment for less than 50% of the dosing prior to 1 year follow-up. In cases of medication error, treatment assignments in the per-protocol analysis will be analyzed according to the actual treatment received as the first study drug dose.

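### SAP 2.3 keeps per-protocol participants by compliance with the randomized product but, after a medication error, assigns their arm by the first dose, so it can place a 75% complier in the opposite arm

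*Combined protocol and SAP*

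**What the plan says.** Section 8.2 has the same text in the original protocol and in protocol v3. It forms the PP set by "excluding participants who complied with the randomized treatment for less than 50% of the follow-up", and then states: "In cases of medication error, treatment assignments in the per-protocol analysis will be analyzed according to the actual treatment received". It does not say which dose decides the arm, and it does not measure compliance in doses.

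The SAP adds both details. SAP v1.0 section 2.3 brings in the first-dose rule, with membership set by "excluding participants who complied with the randomized treatment for less than 50% of the 1 year follow-up". SAP v1.3 section 2.3, the current text, changes membership to "excluding participants who complied with the randomized treatment for less than 50% of the dosing prior to 1 year follow-up". It keeps the rule that, after a medication error, assignments "will be analyzed according to the actual treatment received as the first study drug dose".

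The number of doses comes from protocol v3 section 6.4.3: "At each 6-month interval, a course of 2 doses of study drug will be administered as described above for Day 0 and Day 7". In that section FCM participants who no longer meet the laboratory criteria receive saline by design.

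SAP v1.3 uses the PP set as the key supportive analysis of the primary composite (5.3.1.6), as a supportive analysis of the top secondary outcome (5.3.2.1), and to repeat all its subgroup analyses (5.4). The intent-to-treat (ITT) population, analysed as randomized, is primary for all efficacy analyses (2.1).

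**The concern.** Section 2.3 applies two yardsticks to the same person. Staying in the set depends on how much of the **randomized** product was taken. The arm, after an error, depends on **one dose**, whichever product it was. An as-treated rule normally serves a participant who got the other arm's product for most or all of the trial, but the membership rule has already removed that participant. Those left for the arm rule to act on qualified for the set by taking what they were randomized to.

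A difference in inference between the PP and ITT analyses of the primary composite triggers further exploratory work under 5.3.1.6, so the PP arms should mean what they appear to mean.

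**Working it through.** The documents state no figure that depends on this rule, so there is none to reproduce. The check is to apply the two rules in order to every possible dose pattern.

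**Inputs**
- Planned doses before one year: 4 (Days 0, 7, 180, 187; protocol v3 sections 5.2 and 6.4.3). Counts of 5 and 6 cover the case where some or all of the Day 360/367 course is included (assumption).
- Membership (SAP v1.3, 2.3): keep if R/n ≥ 0.5, where R is the number of doses of the randomized product and n the number planned.
- Arm (SAP v1.3, 2.3): if any dose was the other product (W), the arm is the product given at the first dose.

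**General result.** Kept means R ≥ n/2. Since R + W ≤ n, W ≤ n − R ≤ n/2 ≤ R. No retained participant can have received more of the other product than of the randomized one. Taking doses actually given as the denominator changes nothing: R/(R + W) ≥ 0.5 also gives R ≥ W.

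**Four doses, none missed.** There are 2⁴ − 1 = 15 patterns with at least one error. Kept: 4 with one error + 6 with two = 10. Of these, four begin with W and are moved:

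| Pattern (Days 0, 7, 180, 187) | Randomized product | Kept? | Analysed in |
|---|---|---|---|
| W R R R | 3/4 = 75% | yes | opposite arm |
| W W R R | 2/4 = 50% | yes | opposite arm |
| W R W R | 2/4 = 50% | yes | opposite arm |
| W R R W | 2/4 = 50% | yes | opposite arm |

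The other four patterns that begin with W (three or four wrong doses) have R/n of 25% or 0% and are excluded.

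**Variations** (retained patterns that are moved)
- 4 doses, missed doses allowed: 8, of which 5 are mainly the randomized product, 3 are ties and 0 mainly the other product.
- 5 doses, none missed: 5, all mainly the randomized product.
- 6 doses, none missed: 16, of which 6 are mainly randomized, 10 are ties and 0 mainly the other product.

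These count possible patterns, not expected participants.

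**Comparison with the Safety set.** SAP v1.3 section 2.2 puts anyone who received any FCM in the FCM arm. A participant randomized to FCM with pattern W R R R received three FCM doses. That person is FCM in the Safety set and placebo in PP.

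**Size.** The documents give no error rate. Assume 0.1–0.5% of first doses are wrong: 0.001 × 3014 ≈ 3 and 0.005 × 3014 ≈ 15. This is a ceiling on the number moved, because some of these participants fall below 50% and are excluded. Suppose all 15 are moved, split evenly, with everyone in PP and each moved person keeping the full effect of the randomized product. Then each arm contains 7.5/1507 ≈ 0.5% from the other. The planned 18 m difference in the 6-minute walk test (6MWT) becomes 18 × (1 − 2 × 0.005) = 17.8 m, about 1% smaller. This is a mean-scale illustration; the PP primary analysis is a rank test on the composite.

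**The case against.** **Compliance may be defined elsewhere.** SAP v1.3 section 1 puts important definitions in a supplemental appendix that is not among the documents. If compliance there counted injections of either product, a participant given the other product throughout would stay in PP and the reassignment would do its intended job. This caveat stands, although section 2.3 specifies the randomized treatment. Even so, W R R R would still be kept and still moved by its first dose.

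**The opposite arm is not always the wrong arm.** Three of the four moved patterns are exact ties. In W W R R, both doses before the Day 180 visit, where the 6-month 6MWT is done, were the other product, so as-treated analysis is defensible. Direction matters too: a placebo participant given FCM once in error is FCM under the Safety rule as well. A reader might infer that the rule misplaces compliers in general. The enumeration supports that without argument only for W R R R.

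**Protocol 8.2 might look equally at fault.** It is not: it contains neither the first-dose nor the dosing wording. The point rests on SAP 2.3.

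**Off-protocol iron.** Protocol v3 section 4.7 lists "Use of IV iron outside of protocol" as a concomitant intervention, and a reader might infer that placebo participants who received it should leave the PP set. The documents do not support adding that here. Section 4.7 keeps such participants in the study, SAP 6.3 summarizes these interventions by treatment, and no rate is given. Excluding them from one arm only, on a post-randomization event, could itself introduce bias.

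**The consequence is small.** Agreed. It takes a product error at the first dose, and PP carries no alpha.

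**Conclusion.** Wrong as written, and minor. Within SAP v1.3 section 2.3 the arm rule works against the membership rule: it never moves anyone who mainly received the other product, and it can move someone who took three of four doses as randomized. The conclusion assumes that compliance means receipt of the randomized product, as the text says, and that about four doses fall before one year; it also holds for five or six.

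Few participants are likely to be affected; 3 to 15 is an assumed ceiling, not an estimate. A reader might infer that the trial's main result is at risk. It is not, because the primary and top secondary tests use ITT as randomized. What is affected is the PP analyses in 5.3.1.6, 5.3.2.1 and 5.4.

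**What to change.** In SAP section 2.3, replace the medication-error sentence with: *PP participants are analysed in the arm to which they were randomized; protocol-directed placebo in the FCM arm counts as compliance and is not a medication error.* The second clause matters because FCM participants may properly receive saline from Day 180 onward, and section 2.3 does not say how those doses count.

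Membership and arm would then refer to the same product, and none of the four patterns above would be moved. The cost is one sentence, made before unblinding as the SAP's other changes were, with no new data and no change in who is in the set. The trade-off is that tie cases such as W W R R stay in their randomized arm; a listing of participants with product errors would let readers see how many there are.
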